3.2 Exclusion Criteria

- 3.21 Platinum refractory disease which we define as:
1. Evidence disease progression on platinum based chemotherapy regimen or 2. Evidence of disease progression ≤ 6 months of completion of platinum based adjuvant chemotherapy regimen.
- 3.22 Patient has received prior systemic anti-cancer therapy, tumor embolization or radiotherapy ≤ 28 days prior to registration.
- 3.23 Major surgical procedure, open biopsy, or significant traumatic injury ≤ 28 days prior to registration.
- NOTE: Patients must have recovered from any effects of any major surgery.
- 3.24 Congestive heart failure - New York Heart Association (NYHA) \geq Class II.
- 3.25 Resting ECG indicating uncontrolled, potentially reversible cardiac conditions, as judged by the investigator (eg. unstable ischemia, uncontrolled symptomatic arrhythmia, QTcF prolongation > 500 ms, electrolyte disturbances, etc.), or patients with congenital long QT syndrome. Cardiac arrhythmias requiring anti-arrhythmic therapy.
- NOTE: Pacemaker, beta blockers or digoxin are permitted.
- 3.26 Uncontrolled hypertension – Grade 3 or higher per CTCAE v5.0 (despite optimal medical management).
- 3.27 History of or current pheochromocytoma.
- 3.28 Arterial or venous thrombotic or embolic events such as cerebrovascular accident (including transient ischemic attacks), deep vein thrombosis or pulmonary embolism ≤ 6 months prior to registration.
- 3.29a Ongoing infection $>$ grade 2 NCI-CTCAE v5.0.
- 3.29b Seizure disorder requiring medication.
- 3.29c Symptomatic metastatic brain or meningeal tumors unless the patient is > 6 months from definitive therapy, has a negative imaging study ≤ 28 days of registration and is clinically stable with respect to the tumor at the time of registration. Patients with spinal cord compression unless considered to have received definitive treatment for this and evidence of clinically stable disease for 28 days prior to registration.

NOTE: The patient can receive a stable dose of corticosteroids before and during the study as long as these were started ≤ 28 days prior to registration.

- 3.29d History of organ allograft (including corneal transplant) or allogeneic bone marrow transplant or double umbilical cord blood transplantation (dUCBT).

- 3.29e Evidence or history of bleeding diathesis or any hemorrhage or bleeding event >CTCAE v5.0 grade 3, ≤28 days prior to registration.
- 3.29f Non-healing wound, ulcer, or bone fracture.
- 3.29g Renal failure requiring hemo-or peritoneal dialysis.
- 3.29h Dehydration CTCAE v5.0 grade ≥2.
- 3.29i Substance abuse, medical, psychological or social conditions that may interfere with the patient's participation in the study or evaluation of the study results.
- 3.29j Known hypersensitivity to any of the study drugs, study drug classes, or excipients in the formulation.
- 3.29k Interstitial lung disease with ongoing signs and symptoms at the time of informed consent.
- 3.29l Persistent proteinuria of CTCAE v5.0 Grade 3 or higher (≥ 3.5 g/24 hrs).
- 3.29m Unable to swallow orally administered medications.
- 3.29n Any malabsorption condition and/or patients with gastrointestinal disorders likely to interfere with absorption of the study medication
- 3.29o Unresolved toxicity greater than CTCAE v5.0 Grade 2 attributed to any prior therapy/procedure excluding alopecia and oxaliplatin induced neurotoxicity ≤Grade 2.
- 3.29p Albumin levels <2.5 g/dl.
- 3.29q Any of the following because this study involves an investigational agent whose genotoxic, mutagenic and teratogenic effects on the developing fetus and newborn are unknown.
 - Pregnant women
 - Nursing women
 - Men or women of childbearing potential who are unwilling to employ adequate contraception

NOTE: Women of childbearing potential and their partners, who are sexually active, must agree to the use of TWO highly effective forms of contraception in combination (as described in Appendix V). This should be started from the time of registration and continue throughout the period of taking study treatment and for at least 1 month after last dose of study drug(s), or they must totally/truly abstain from any form of sexual intercourse (as described in Appendix V).

Male patients must use a condom during treatment and for 3 months after the last dose of olaparib when having sexual intercourse with a pregnant woman or with a woman of childbearing potential. Female partners of male patients should also

use a highly effective form of contraception (as described in Appendix V) if they are of childbearing potential. Male patients should not donate sperm throughout the period of taking olaparib and for 3 months following the last dose of olaparib.

- 3.29r Co-morbid systemic illnesses or other severe concurrent disease which, in the judgment of the investigator, would make the patient inappropriate for entry into this study or interfere significantly with the proper assessment of safety and toxicity of the prescribed regimens. Patients considered a poor medical risk due to a serious, uncontrolled medical disorder, non-malignant systemic disease or active, uncontrolled infection. Examples include, but are not limited to, uncontrolled ventricular arrhythmia, recent (within 3 months) myocardial infarction, uncontrolled major seizure disorder, unstable spinal cord compression, superior vena cava syndrome, extensive interstitial bilateral lung disease on High Resolution Computed Tomography (HRCT) scan or any psychiatric disorder that prohibits obtaining informed consent.

- 3.29s Immunocompromised patients and patients known to be HIV serologically positive and currently receiving antiretroviral therapy.

NOTE: Patients known to be HIV positive, but without clinical evidence of an immunocompromised state, are eligible for this trial.

- 3.29t Receiving any other investigational agent which would be considered as a treatment for the primary neoplasm.

- 3.29u Previous and/or intercurrent cancers. With the exception of: curatively-treated cancers with no recurrence in ≥ 5 years or early cancers treated with curative intent, including but not limited to cervical carcinoma in situ, superficial, noninvasive bladder cancer, basal cell carcinoma, squamous cell carcinoma in situ, , , ductal carcinoma in situ (DCIS), Stage 1, grade 1 endometrial carcinoma, or endoscopically resected gastrointestinal cancers limited in mucosal layer.

NOTE: All cancer treatments for cancers that were distinct in a primary site other than biliary tract cancer must be completed ≥ 3 years prior to registration.

- 3.29v Pleural effusion or ascites that causes respiratory compromise (\geq CTCAE v5.0 Grade 2 dyspnea).

- 3.29w Previous enrollment in the present study

- 3.29x Prior exposure to any PARP inhibitor including olaparib.

- 3.29y Known hypersensitivity reaction to olaparib or any of the excipients of the product.

- 3.29z Myelodysplastic syndrome/acute myeloid leukemia or with features suggestive of MDS/AML.

- 3.29aa Concomitant use of known strong CYP3A inhibitors (eg. itraconazole, telithromycin, clarithromycin, protease inhibitors boosted with ritonavir or cobicistat, indinavir, saquinavir, nelfinavir, boceprevir, telaprevir) or moderate CYP3A inhibitors (eg. ciprofloxacin, erythromycin, diltiazem, fluconazole, verapamil).

NOTE: The required washout period prior to registration is 2 weeks.

- 3.29ab Concomitant use of known strong (eg. phenobarbital, enzalutamide, phenytoin, rifampicin, rifabutin, rifapentine, carbamazepine, nevirapine and St John's Wort) or moderate CYP3A inducers (eg. bosentan, efavirenz, modafinil).

NOTE: The required washout period prior to registration is 5 weeks for enzalutamide or phenobarbital and 3 weeks for other agents.

- 3.29ac Patient taking medications or herbal products including grapefruits, grapefruit hybrids, pomelos, star fruits, Seville oranges, pomegranates, or the juice from any of these. Note: Patients must discontinue the drug/product ≥ 7 days prior to registration.
- 3.29ad Patient taking medications with a known risk to prolong the QTc interval and/or cause Torsades de Pointes. Note: Patients must be discontinued ≥ 7 days of registration. Treating physicians may wish to replace the drug(s) that do not carry this risk with safe alternative(s).
- 3.29ae Whole blood transfusions in the last 120 days prior to entry to the study (packed red blood cells and platelet transfusions are acceptable outside of 28 days prior to treatment)
- 3.29af Involvement in the planning and/or conduct of the study
- 3.29ag Judgment by the investigator that the patient should not participate in the study if the patient is unlikely to comply with study procedures, restrictions, and requirements

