3.0 Patient Eligibility

NOTE: Waivers to eligibility criteria are not allowed per ACCRU policy

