6.23 Correlative Research

Mandatory

A mandatory correlative research component is part of this study. The patient will be automatically registered onto this component (see Sections 3.0, 14.0 and 17.0).

Optional

An optional correlative research component is part of this study, there will be an option to select if the patient is to be registered onto this component (see Section 17.0).

- Patient has/has not given permission to give his/her tissue sample for research testing.

6.24 At the time of registration, the following will be recorded:

- Patient has/has not given permission to store and use his/her sample(s) for future research to learn about, prevent, or treat cancer.
- Patient has/has not given permission to store and use his/her sample(s) for future research to learn, prevent, or treat other health problems (for example: diabetes, Alzheimer's disease, or heart disease).
- Patient has/has not given permission for ACCRU to give his/her sample(s) to outside researchers.

6.25 Treatment cannot begin prior to registration and must begin ≤ 7 days after registration.

6.26 Pretreatment tests/procedures (see Section 4.0) must be completed within the guidelines specified on the test schedule.

6.27 All required baseline symptoms (see Section 10.5) must be documented and graded.

6.28 Treatment on this protocol must commence at an ACCRU institution under the supervision of a medical oncologist.

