
 • CYP3A4 substrates: hormonal contraceptive, simvastatin, cisapride, cyclosporine, ergot alkaloids, fentanyl, pimozone, sirolimus, tacrolimus and quetiapine • CYP2B6 substrates: bupropion, efavirenz • OATP1B1 substrates: bosentan, glibenclamide, repaglinide, statins and valsartan • OCT1, MATE1 and MATE2K substrates: metformin • OCT2 substrates: serum creatinine • OAT3 substrates: furosemide, methotrexate 	
Effect of olaparib on other drugs
 
Based on limited in vitro data, olaparib may increase the exposure to substrates of CYP3A4, OATP1B1, OCT1, OCT2, OAT3, MATE1 and MATE2K.
 
Based on limited in vitro data, olaparib may reduce the exposure to substrates of 2B6.
 
Caution should be observed if substrates of these isoenzymes or transporter proteins are co-administered.

Anticoagulant therapy	
Patients who are taking warfarin may participate in this trial; however, it is recommended that international normalized ratio (INR) be monitored carefully at least once per week for the first month, then monthly if the INR is stable. Subcutaneous heparin and low molecular weight heparin are permitted.

Palliative radiotherapy	
Palliative radiotherapy may be used for the treatment of pain at the site of bony metastases that were present at baseline, provided the investigator does not feel that these are indicative of clinical disease progression during the study period. Study treatment should be discontinued for a minimum of 3 days before a patient undergoes therapeutic palliative radiation treatment. Study treatment should be restarted within 4 weeks as long as any bone marrow toxicity has recovered.

Administration of other anti-cancer agents	
Patients must not receive any other concurrent anti-cancer therapy, including investigational agents, while on study treatment. Patients may continue the use of bisphosphonates or denosumab for bone disease and corticosteroids for the symptomatic control of brain metastases provided the dose is stable before and during the study and they were started at least 4 weeks prior to beginning study treatment.

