13.0 Treatment/Follow-up Decision at Evaluation of Patient

- 13.1 A patient is deemed *ineligible* if after registration, it is determined that at the time of registration, the patient did not satisfy each and every eligibility criteria for study entry.
- If the patient received treatment, the patient may continue treatment at the discretion of the physician as long as there are not safety concerns. The patient will continue in the Active Monitoring/Treatment phase of the study, as per section 4.0 of the protocol.
 - If the patient never received treatment, on-study material must be submitted.
- 13.2 A patient is deemed a *major violation*, if protocol requirements regarding treatment in cycle 1 of the initial therapy are severely violated that evaluability for primary end point is questionable. If the patient received treatment, the patient may continue treatment at the discretion of the physician as long as there are no safety concerns. The patient will continue in the Active Monitoring/Treatment phase of the study, as per section 4.0 of the protocol, and all data submission should continue per protocol. If the patient does not continue with treatment, the patient will go Off Treatment and be followed in Survival Follow-up
- 13.3 A patient is deemed a *cancel* if he/she is removed from the study for any reason before any study treatment is given. On-study material and the End of Active Treatment/Cancel Notification Form must be submitted. No further data submission is necessary.
- 13.4 Patients will continue treatment until progression or a maximum of 36 cycles, unacceptable adverse events, or patient refusal. Treatment will then be discontinued and the patient will go to event monitoring and be followed per Section 18.0.
- 13.5 Patients who are CR, PR, or SD will continue treatment per protocol or a maximum of 36 cycles.

- 13.6 Patients who develop PD while receiving therapy will go to the event-monitoring phase and will be followed for survival (i.e. event-monitoring phase) every 3 months (± 7 days) for 3 years after registration (per Section 18.0).
- 13.7 Patients who go off protocol treatment for reasons other than PD will go to the event-monitoring phase and be followed for survival and progression (i.e. event monitoring phase) every 3 months (± 7 days) for 3 years after registration (per Section 18.0).

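### Steroid timing for brain metastases: Section 3.29c sets a 28-day maximum before registration and Section 9.5 a 4-week minimum before treatment; the 3.29c sign appears reversed

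*Combined protocol and SAP*

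**What the plan says.** Criterion 3.29c excludes symptomatic brain or meningeal tumours, and spinal cord compression, with stated exceptions. Its NOTE then says: "The patient can receive a stable dose of corticosteroids before and during the study". It attaches one condition, on timing: "as long as these were started ≤ 28 days prior to registration".

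The last row of the restricted-medication table in Section 9.5 permits "corticosteroids for the symptomatic control of brain metastases provided the dose is stable before and during the study", on the further condition that "they were started at least 4 weeks prior to beginning study treatment".

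The two rules are anchored differently, one at registration and the other at first dose. Section 6.25 links the anchors: treatment cannot precede registration and "must begin ≤ 7 days after registration".

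Three other places decide what follows from a failed criterion. Section 3.0 states: "Waivers to eligibility criteria are not allowed per ACCRU policy". Section 13.1 classes a patient as ineligible if it is later found that, at registration, "the patient did not satisfy each and every eligibility criteria for study entry". Section 16.21 limits the evaluable set for the primary endpoint to patients who are eligible, consented and treated.

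**The concern.** Both rules require a stable dose and both use the same four-week figure, but their inequalities point in opposite directions. The NOTE admits a patient who began steroids the day before registration and turns away one who has been stable on them for three months. That is the reverse of what a stable-dose condition is meant to secure.

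Two separate effects follow from the text as written.

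1. **Eligibility.** A patient whose steroids began more than 28 days before registration is allowed by 9.5 but fails the NOTE. No waiver is available. If the patient is enrolled and treated anyway, 13.1 makes the patient ineligible and 16.21 removes the patient from the primary analysis.
2. **Concomitant medication.** A patient who started recently meets 3.29c, and so remains eligible and evaluable, but breaches 9.5 at the first dose.

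Only the first effect touches eligibility. Section 9.5 does not put this timing limit on steroids for other purposes, such as antiemetic dexamethasone or cord compression, so the clash does not extend to them.

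**Working it through.** The plan gives no figure to reproduce here; the check is a count of days.

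**Inputs**
- x = days from steroid start to registration.
- d = days from registration to first dose, 0 to 7 (Section 6.25).
- 3.29c NOTE as written: x ≤ 28.
- Section 9.5: x + d ≥ 28, taking 4 weeks as 28 days.

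**Both rules together.** x must lie between 28 − d and 28.

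| Lag d (days) | Values of x meeting both rules | Number of days |
|---|---|---|
| 0 | 28 | 1 |
| 1 | 27–28 | 2 |
| 2 | 26–28 | 3 |
| 3 | 25–28 | 4 |
| 4 | 24–28 | 5 |
| 5 | 23–28 | 6 |
| 6 | 22–28 | 7 |
| 7 | 21–28 | 8 |

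**The 29 start days that 3.29c admits (x = 0 to 28)**
- x = 0 to 20 (21 days): even at d = 7, x + d ≤ 27, so 9.5 is always breached.
- x = 21 to 27 (7 days): the result depends on the lag.
- x = 28 (1 day): both rules are always met.
- Check: 21 + 7 + 1 = 29.

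Every start with x > 28 meets 9.5 and fails 3.29c. The difference in anchors therefore leaves an overlap of 1 to 8 days and does not reconcile the rules.

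**With the sign reversed (x ≥ 28).** Since d ≥ 0, x + d ≥ 28 for every permitted lag, so the timing condition in 9.5 is always met.

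**Which rule is wrong**
- Section 9.5 gives its direction in words, so a flipped symbol cannot explain it.
- A minimum time on steroids fits a stable-dose condition; a maximum does not.
- The cord-compression part of 3.29c uses 28 days as a minimum: "evidence of clinically stable disease for 28 days prior to registration".
- Exclusions 3.22 and 3.23 use ≤ 28 days before registration to keep out recent events. The NOTE grants a permission, so the sign should turn round. Carry-over from that exclusion phrasing is a plausible cause, though this is an inference.

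**The case against.** The wording and the arithmetic are not in dispute. The objections concern how much can be built on them.

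- **One character carries the point.** Other limits in Section 3 are not fully reliable: 3.17 shows a creatinine clearance limit of ≥ 1 mL/min, while the renal-impairment text in Section 8.2 gives the inclusion threshold as ≥ 51 mL/min. This stands as a reason to check the source PDF and to hold the inference with medium confidence. The neighbouring signs in 3.22, 3.23 and 3.28 do read sensibly.
- **The NOTE is worded as a permission.** No section says in terms that falling outside a NOTE means failing the criterion. However, the permission carries an express condition and sits inside an exclusion criterion that cannot be waived. Reading it as binding is fair, and a site checking eligibility would have to treat it so.
- **The group is very small.** Symptomatic brain disease is admitted only more than 6 months after definitive therapy, with negative imaging and clinical stability. Few such patients would need steroids for symptoms, and for patients without symptoms it is unclear whether the NOTE applies. This stands and limits the severity.
- **The use of 28 days within 3.29c is mixed.** The imaging condition uses ≤ 28 days as a recency limit. This stands, so the cord-compression wording is only supporting evidence; the stable-dose wording and 9.5 carry the argument.
- **The corrected rule reaches further than 9.5.** It would turn away starts 21 to 27 days before registration that could meet 9.5 with a later first dose, and it would also cover cord-compression steroids. Both are true and cost little. Eligibility is settled at registration, so a limit anchored there is the workable one, and the cord-compression exception already requires 28 days of stable disease.

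**Conclusion.** The inconsistency is real and the concern holds. As written, the two rules agree only for steroid starts 21 to 28 days before registration, depending on the lag, and the NOTE turns away the long-standing stable-dose patient whom 9.5 permits. That the error lies in 3.29c is a well-supported inference; the text alone does not prove it.

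Severity is minor. The documents give no frequency for brain metastases or for steroid use in them, so the number affected cannot be calculated. Given how tightly 3.29c restricts symptomatic cases, it would be few and possibly none of the 36. Section 16.22 already allows 6 patients beyond the 30 evaluable for ineligibility, cancellation and other losses. The two-stage boundaries, the type I error of 0.091 and the power of 80.6% do not depend on this rule.

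The conclusion assumes that the ≤ sign is present in the source PDF and that the NOTE's condition is binding.

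**What to change.** First check the sign in the source PDF and confirm the intent with the clinical team. If the sign is as shown and a minimum was meant, change the 3.29c NOTE to *started ≥ 28 days prior to registration*. Dose stability remains a separate condition in both places.

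If the clinical team does not want the minimum to apply to cord-compression steroids, the same edit can limit the NOTE to steroids for brain metastases.

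The cost is one character at the next amendment, or a few words with the optional limit. Sample size, error rates and analysis are unaffected.

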4.0 Test Schedule

Tests and procedures	Active Monitoring Phase					
	≤7 days prior to registration	Cycle 1 (+/- 7 days)	Cycle 2 (+/- 7 days)	After Cycle 2, Day 1 of every cycle until progression (+/- 7 days)	End of Treatment (at PD, withdrawal, or removal)	30 days after last dose of study drug (+/- 7 days)
		Week1 (Day 1)	Week 1 (Day 1)			
History and exam, weight, ECOG PS ⁷ , blood pressure	X	X ⁷	X	X	X	X
Height	X					
Adverse event assessment	X	X	X	X	X	X
Hematology ⁵ : CBC/ differential, ANC, MCV, INR/aPTT	X	X	X	X	X	
Chemistry ⁵ : SGOT (AST), alk phos, T. bili, serum creatinine, calcium, glucose, Na, K, SGPT (ALT)	X	X	X	X	X	
Albumin, serum total protein ⁵	X		X			
Urinalysis- White blood cells, red blood cells, protein, glucose, hyaline casts	X					
Tumor measurement (CT scan of chest, abdomen and pelvis) (MRI if CT is not feasible)	X ¹			X ¹	X ^{1,6}	
ECG ⁴	X					
Serum pregnancy test	X ²	X	X	X	X	
Mandatory Plasma blood collection (see Section 14.1) ^R		X		X ¹⁰	X	
Mandatory archival tissue sample (see Section 17.0) ^{8, R}		X				
Optional tissue sample (see Section 17.0) ^{9,R}					X	
Patient Medication Diary (Appendix II) ³		X	X	X	X	

1. CT scans preferred (MRI if CT is not feasible) of the chest, abdomen and pelvis. Use same imaging throughout the study. Tumor measurements at baseline (≤ 28 days prior to registration) and every 8 weeks until progression.
 2. For women of childbearing potential only. Pregnancy tests on blood or urine samples will be performed for women of childbearing potential within 28 days prior to the start of study treatment, on Day 1 of the study prior to commencing treatment and at each subsequent visit during study treatment and at the 30 day follow up visit. Tests will be performed by the hospital's local laboratory. If results are positive the patient is ineligible/must be discontinued from study treatment immediately. Details of the pregnancy tests must be recorded in the patient's medical records.
 3. The diary must begin the day the patient starts taking the medication and must be completed per protocol and returned to the treating institution during each scheduled visit.
 4. Performed at screening and then as needed.
 5. Hematology and chemistry tests to be done prior to each cycle. Activated partial thromboplastin time (APTT) will be performed at screening and if clinically indicated. International normalized ratio (INR) will be performed at screening and if clinically indicated. Each coagulation test result will be recorded in CRF. In case a patient shows an AST or ALT $\geq 3 \times$ ULN together with total bilirubin $\geq 2 \times$ ULN please refer to Appendix 'Actions required in cases of increases in liver biochemistry and evaluation of Hy's Law' for further instructions.
 6. If patient goes off study during Cycle 1 and last CT scan was done > 28 days prior, the CT scan must be done.
 7. If baseline history, exam, weight, ECOG PS, and blood pressure were performed ≤ 3 days of Cycle 1 Day 1, they do not need to be repeated for Cycle 1 Day 1.
 8. Archival tissue will be collected ≤ 28 after registration. Patients may initiate study treatment prior to the receipt of the archival tissue. See section 17.
 9. Optional tissue collection at end of treatment.
 10. At the time of radiographic assessment (Every 8 weeks).
- R Research funded.

5.0 Stratification Factors OR Grouping Factor:

None

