10.31 EXPECTED Serious Adverse Events: Protocol Specific Exceptions to Expedited Reporting

For this protocol only, the following Adverse Events/Grades are expected to occur within this population and do not require Expedited Reporting. These events must still be reported via Routine Reporting (see Section 10.53). *

System Organ Class (SOC)	Adverse event/ Symptoms	CTCAE Grade at which the event will not be expeditedly reported.
Gastrointestinal Disorders	Diarrhea	Any Grade
	Dyspepsia	
	Nausea	
	Vomiting	
	Colitis	Grades 1-3
	Pancreatitis	
General disorders and administrations site conditions	Fatigue (asthenia, lethargy, malaise)	Any Grade
Hepatobiliary disorders	Cholecystitis	Grades 1-3
Infections and infestations	Lung Infection	Grades 1-3
	Sinusitis	
	Skin infection	
	Urinary tract infection	
Investigations	Alkaline phosphatase increased	Any Grade
	Alanine aminotransferase increased	
	Aspartate aminotransferase increased	
	Lymphocyte count decreased	
	Weight loss	
Metabolism and nutrition disorders	Anorexia	Any Grade
	Dehydration	
	Hyperkalemia	
	Hypocalcemia	

Musculoskeletal and connective tissue disorders	Hypomagnesemia	Any Grade
	Hyponatremia	
	Arthralgia	
	Back pain	
Skin and subcutaneous tissue disorders	Musculoskeletal and connective tissue disorder – Other (muscle spasms)	Any Grade
	Alopecia	
	Rash acneiform	
	Rash maculo-papular	
	Palmar-plantar erythrodysesthesia syndrome	

These exceptions only apply if the adverse event does not result in hospitalization. If the adverse event results in hospitalization, then the standard expedited adverse events reporting requirements must be followed.

The following hospitalizations are not considered to be SAEs because there is no “adverse event” (i.e., there is no untoward medical occurrence) associated with the hospitalization:

- Hospitalizations for respite care
- Hospitalization planned before informed consent (where the condition requiring the hospitalization has not changed post study drug administration)
- Hospitalization for routine maintenance of a device (e.g., battery replacement) that was in place before study entry

*Report any clinically important increase in the **rate** of a serious suspected adverse reaction (at your study) site over that which is listed in the protocol or investigator brochure as an expedited event.

*Report an expected event that is greater in severity or specificity than expected as an expedited event

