Olaparib may modulate the exposure to substrates of OATP1B1 (eg, bosentan, glibenclamide, repaglinide, statins and valsartan), OCT1 (eg, metformin), OCT2 (eg, serum creatinine), OAT3 (furosemide, methotrexate), MATE1 and MATE2K (metformin). In particular, caution should be exercised if olaparib is administered in combination with any statin.

Co-administration of topotecan reduced steady state exposure to olaparib by approximately 20%.

15.17 **Known potential toxicities:**

Very Common potential toxicities (> 10%):

Cardiovascular: Peripheral edema, edema

Central nervous system: Fatigue, headache, dizziness

Dermatologic: Dermatitis, skin rash

Endocrine & metabolic: Hypomagnesemia

Gastrointestinal: Nausea, abdominal pain, vomiting, diarrhea), dysgeusia, dyspepsia, constipation, decreased appetite, stomatitis, upper abdominal pain

Genitourinary: Urinary tract infection

Hematologic & oncologic: Increased MCV, decreased absolute lymphocyte count, anemia, decreased platelet count, neutropenia, leukopenia

Infection: Influenza

Neuromuscular & skeletal: Weakness, musculoskeletal pain, arthralgia, myalgia,

back pain

Renal: Increased serum creatinine

Respiratory: Nasopharyngitis, respiratory tract infection, rhinitis, sinusitis, cough, dyspnea

Miscellaneous: Fever

Common potential toxicities, 1% to 10%:

Cardiovascular: Hypertension, venous thrombosis (embolism)

Central nervous system: Anxiety, depression, insomnia, peripheral neuropathy

Dermatologic: Pruritus, xeroderma (including eczema)

Endocrine & metabolic: Hot flash, hyperglycemia

Genitourinary: Dysuria, urinary incontinence, vulvovaginal disease

Hematologic & oncologic: Myelodysplastic syndrome

Uncommon potential toxicities, <1%: Hypersensitivity reaction, pneumonitis

- 15.18 **Drug procurement:** AstraZeneca will supply the drug to Clinical Research Services, a division of Rx Crossroads by McKesson. Each participating ACCRU treating location will order the drug from Clinical Research Services. Submit the Drug Order Request Form (found on the ACCRU web site) to:

Each participating ACCRU treating location will be responsible for monitoring the supply of olaparib and will use the Drug Order Request Form to order additional supplies as needed.

Outdated or remaining drug is to be destroyed on-site as per procedures in place at each institution.

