16.34 Duration of Response

Duration of response (DoR) is defined for all evaluable patients who have achieved an objective response as the date at which the patient's earliest best objective status is first noted to be either a CR or PR to the earliest date progression is documented, or death if no prior evidence of disease progression. The distribution of DoR will be estimated using the method of Kaplan-Meier. The median DoR and corresponding 95% confidence interval will be reported.

16.354 Adverse Events

All patients who have initiated treatment will be considered evaluable for adverse event analyses. Adverse events by patient will be summarized by frequencies and severity using CTCAE version 5.0. The proportion of patients who experience at least one grade 3+ adverse event (regardless of attribution) will be reported.

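### Hypomagnesemia is listed as a toxicity above 10% and as routinely reportable, but no scheduled test measures magnesium, so its reported frequency will depend on ad hoc local testing

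*Combined protocol and SAP*

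**What the plan says.** Section 4.0 has two chemistry rows. The main one reads "SGOT (AST), alk phos, T. bili, serum creatinine, calcium, glucose, Na, K, SGPT (ALT"). It is marked at screening, on Day 1 of each cycle and at end of treatment. The other is "Albumin, serum total protein", marked at screening and Cycle 2. Footnote 5 sets the timing ("Hematology and chemistry tests to be done prior to each cycle") and adds no analyte.

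Section 15.17 lists "Endocrine & metabolic: Hypomagnesemia" in the class headed "Very Common potential toxicities (> 10" percent). Section 10.31 includes "Hypomagnesemia" among the expected events exempt, at any grade, from expedited reporting unless they lead to hospitalization, and adds: "These events must still be reported via Routine Reporting (see Section 10.53").

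The events solicited at each visit under Section 10.52 are diarrhea, nausea, vomiting, fatigue, palmar-plantar erythrodysesthesia, maculo-papular rash and hypertension. For anything else, Section 10.53 collects grade 2 events that are at least possibly related, all grade 3 and 4 events, and deaths.

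The analysis in Section 16.354 serves objective 2.25: "Adverse events by patient will be summarized by frequencies and severity using CTCAE version 5.0". It also reports the proportion of patients with at least one grade 3 or higher event.

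**The concern.** Hypomagnesemia is found and graded from a blood value. The plan expects it in more than one patient in ten and wants it reported when it occurs, but schedules nothing that would reveal it. Adverse events are assessed at every visit, but that brings a low magnesium to light only if someone has ordered the test.

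Three outputs could be affected: the hypomagnesemia line of the Section 16.354 table, the grade 3 or higher proportion, and, for related grade 3 or higher cases, the accrual-suspension rule in Section 16.52. That rule is triggered by as few as 2 of the first 20 treated patients. Attribution is weakened too. No baseline magnesium is scheduled, so a low value on treatment cannot be compared with a pre-treatment one, and attribution decides whether a grade 2 event is collected at all.

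**Working it through.** The plan states no figure that depends on magnesium testing, so there is nothing to reproduce. The check is a comparison of sections, followed by illustrative counts.

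**Step 1. Events defined by a blood value, set against the schedule.**

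| Event in 10.31 or 15.17 | Scheduled test in 4.0 |
|---|---|
| AST, ALT, alkaline phosphatase increased | AST, ALT, alk phos |
| Hyperkalemia, hyponatremia, hypocalcemia | K, Na, calcium |
| Hyperglycemia | glucose |
| Creatinine increased | serum creatinine |
| Anemia, low platelets, neutropenia, leukopenia, low lymphocytes, raised MCV | CBC with differential, ANC, MCV |
| Hypomagnesemia | none |

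Hypomagnesemia is the only one without a test, and no reason is given.

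**Step 2. Number of treated patients.** Section 16.22 gives 30 evaluable patients plus 6 for ineligibility, cancellation or other reasons, so maximum accrual is 30 + 6 = 36. A cancelled patient has had no study treatment (Section 13.3), and the adverse event population is those who started treatment. If both stages fill, the treated number lies between 30 and 36.

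**Step 3. Illustrative count.** Take p = 0.10, the edge of the frequency class in 15.17.

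- Expected cases: 30 × 0.10 = 3.0; 36 × 0.10 = 3.6.
- Chance of at least one case: 1 − 0.9^30 = 0.958; 1 − 0.9^36 = 0.977.

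**Step 4. Dependence on unscheduled testing.** Let q be the share of true cases found by local testing. The expected observed count is n × 0.10 × q, and the chance of seeing none is (1 − 0.10q)^n. With n = 36:

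| q | Expected observed | Chance of none observed |
|---|---|---|
| 0 | 0 | 1.000 |
| 0.25 | 0.9 | 0.402 |
| 0.50 | 1.8 | 0.158 |
| 0.75 | 2.7 | 0.060 |
| 1 | 3.6 | 0.023 |

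The documents do not give q, so the understatement has no computable size.

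**Step 5. What a scheduled test would add.** Section 10.53 would still omit unsolicited grade 1 and unrelated grade 2 events. The gain is related grade 2 and all grade 3 and 4 events. Section 15.17 gives no split by grade, so the counts in Steps 3 and 4 are not counts of recoverable events.

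**Step 6. The suspension rule.** Let r be the rate of related grade 3 or higher hypomagnesemia (assumed; not in the documents). The chance that this event alone reaches 2 of 20 is 1 − (1 − r)^20 − 20r(1 − r)^19:

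- r = 0.01: 0.017
- r = 0.02: 0.060
- r = 0.05: 0.264

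Missed cases would therefore bear on the rule mainly if severe related cases are not rare.

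**The case against.** The strongest reply is that the plan leaves room to find the event. Nothing bars a site from measuring magnesium when it sees a reason to, and any value obtained can be graded under CTCAE v5.0, reported under Section 10.53 and tabulated. This stands, and it rules out two readings that a reader might infer: that hypomagnesemia cannot be graded in this trial, and that its reported rate will be near zero. Only cases never tested go ungraded, and the rate depends on the unknown q.

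It can also be said that Section 10.31 is an exemption from expedited reporting and does not promise to screen for each listed term; that the chemistry row is not the only filter, since 10.52 and 10.53 also limit what is collected; and that Section 18.1 lists a laboratory results form at baseline only. All of this is correct. It limits what the fix recovers, but it does not explain why one listed laboratory event has no scheduled test when all the others do.

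A reader might further infer a patient-safety gap from Section 9.4, which calls for correction of electrolyte imbalances in severe diarrhea. That section concerns clinically directed care of affected patients. It does not show that magnesium would go unmeasured in them, and no figure in the documents supports a safety consequence.

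Lastly, this is one adverse event line in a single-arm phase II trial of a drug whose safety profile Section 16.52 calls well established. That bears on severity and is accepted.

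**Conclusion.** The inconsistency is real and narrow. Sections 10.31 and 15.17 treat hypomagnesemia as common and reportable, while Sections 4.0 and 10.52 provide no systematic way to detect it. Its reported frequency and severity are likely, though not certain, to be understated. At an assumed true rate of 10% in 36 treated patients, the expected observed count could lie anywhere from 0 to 3.6. That illustration rests on full accrual and on reading the 15.17 class as a patient-level rate applicable to this trial; the documents do not specify its grade or population.

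The effect is confined to one line of the adverse event table, the grade 3 or higher proportion and possibly the Section 16.52 rule. The primary endpoint, the two-stage decision rule and the sample size are untouched. Severity: minor.

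**What to change.** Add magnesium to the Chemistry row of Section 4.0 at the time points already marked (screening, Day 1 of each cycle, end of treatment), and state that it serves adverse event ascertainment. No treatment rule is needed or proposed. Include the analyte on the baseline laboratory form named in Section 18.1, so that a pre-treatment value is on file. On-treatment findings would reach the database through the adverse event forms, within the limits of Section 10.53.

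The cost is a small laboratory charge per draw, on blood already being taken, with no extra visit, procedure or patients.

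If sampling can no longer be changed, state in the adverse event report that hypomagnesemia was not systematically ascertained, so that a low count is not read as absence of the toxicity.
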